10.4 Interim Analyses to Ensure Patient Safety

We will use the method for interim analyses described by Emerson and Fleming to provide cut-points for an interim analysis for futility.

We use the following notions to describe the interim analyses plan.

Let p represent the true insulin independence rate 75 days after the first single donor islet infusion. The efficacy hypothesis is

$$H_{01}: p \leq 0.167 \text{ versus } H_{a1}: p > 0.167.$$

Rejecting this null hypothesis would lead to concluding that 75 day insulin independence rate is better than 16.7% in patients who receive AAT. In order to ensure that the study provides the maximum safety information, this study will not be stopped for efficacy.

The futility hypothesis is

$$H_{02}: p \geq 0.60 \text{ versus } H_{a2}: p < 0.60.$$

Rejecting this hypothesis would lead to concluding that 75 day insulin independence rate in patients who receive AAT is not greater than 0.60. The type II error (accepting the null hypothesis when it is false) is no greater than 0.025.

Table 10 assumes two equally spaced analyses; an interim analysis is planned when 10 subjects have completed the study and a final analysis will happen when all 20 subjects have completed the study. The table provides cut-points for a recommendation for futility (reject H_{02}). Column 3 in this table (labeled “Number of insulin independence at 75 days required”) provides the largest number of observed 75 day insulin independence that would lead to recommending futility.

At the first interim analysis (when 10 subjects have completed the study) the monitoring plan would recommend for futility if no more than 2 of the first 10 transplant subjects demonstrate a insulin

independence at 75 days after their transplant.

Table 10: Sequential Monitoring Plan

Patients Accrued Fixed Sample		Number of insulin independence at 75 days required*
10	Reject H_{02}	≤ 1
20	Accept H_{01}	≤ 7

* Based on exact binomial probabilities

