10.3 Sample Size and Power Calculations

10.3.1 Power for Primary Endpoint

The primary end-point is the rate of insulin independence 75 days after the first single donor islet infusion. Our hypothesis is that the greater engrafted mass achieved with AAT will result in a significant increase in the proportion of subjects achieving insulin independence after the first dose. In the Edmonton era, single donor insulin independence occurred in less than 10% of patients. It appears that this is increased in patients treated with T cell depletion and Etanercept to 18%. In the CIT06 study patient who received islet transplantation after kidney grafting showed an insulin independence rate of 16.7%. A similar rate of insulin independence in IAK patients is seen in the CITR registry.

Table 7 gives the statistical power to reject the null hypothesis that the insulin independence rate is $\leq 16.7\%$, assuming a sample size of 20, using one-sided binomial test with 2.5% type 1 error. Sample size calculations assume asymptotic normality. We propose that AAT treatment will achieve single donor insulin independence in 50% of patients. With 20 patients we will have approximately an 87% power to reject the null hypothesis that the insulin independence rate is $\leq 16.7\%$ using a one-sided binomial test with 2.5% type 1 error. We believe the insulin independence rate after the first single donor islet infusion is at least as high as the control (reported in the CIT-06 study) using a one-sided test. If the true insulin independence rate is 55%, we would have 94% power to reject the null hypothesis. This suggests that we have a good chance of finding meaningful trends and potentially statistically significant differences between groups using highly relevant clinical end points in this pilot trial.

Table 7 Statistical Power to Reject the Null Hypothesis

True insulin independence rate in the study	Statistical power
45%	75%
50%	87%
55%	94%
60%	98%

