We have chosen to transplant 20 subjects. This will provide approximately 87% power to detect a difference of 50% insulin independence rate in islet transplanted subjects versus the estimated 16.7% insulin independence rate. Table 8 displays minimal detectable differences with 70%, 80% and 90% power. The smallest difference that can be detected with 90% power by a one-sided 2.5% level binomial test is 52% compared to 16.7%. The minimal detectable difference is 47% compared to 16.7% with 80% power. Using a one-sided test with 10% type 1 error rate, we could detect a medium effect of slightly more than 2 fold difference (38% vs. 16.7%) with 70% power.

Table 8 Minimum Detectable Difference for Insulin Independence Rate

Power	Minimum detectable difference
70%	43% vs. 16.7%
80%	47% vs. 16.7%

90%	52% vs. 16.7%
-----	---------------

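### Section 10.4 gives a type II error limit of 0.025 without a rate, two different interim cut-points, and a final row that accepts H01 at counts which do not exclude the 50% target

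*Combined protocol and SAP*

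**What the plan says.** Section 10.3.1 sets the design rate: "We propose that AAT treatment will achieve single donor insulin independence in 50% of patients". The power calculation is made "assuming a sample size of 20, using one-sided binomial test with 2.5% type 1 error", with H01 set at a rate of 16.7% or less, and it reports: "With 20 patients we will have approximately an 87% power to reject the null hypothesis". Table 7 lists power of 75%, 87%, 94% and 98% at true rates of 45%, 50%, 55% and 60%.

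Section 10.4 restates the efficacy hypothesis ("Rejecting this null hypothesis would lead to concluding that 75 day insulin independence rate is better than 16.7% in patients who receive AAT") and rules out stopping for efficacy. It adds a futility hypothesis, H02: p ≥ 0.60, of which it says: "Rejecting this hypothesis would lead to concluding that 75 day insulin independence rate in patients who receive AAT is not greater than 0.60". The next sentence reads: "The type II error (accepting the null hypothesis when it is false) is no greater than 0.025". It names no rate, and no reason is given for using 0.60 rather than 0.50.

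The text describes column 3 of Table 10 as the largest count that leads to a futility recommendation, that is, to rejecting H02. The table prints *Reject H02* at ≤1 of 10 and *Accept H01* at ≤7 of 20. The paragraph just above the table recommends futility at no more than 2 of the first 10. A footnote says the cut-points come from exact binomial probabilities.

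**The concern.** Section 10.4 holds the decision table for the primary endpoint, and Section 6.2.1 points the DSMB to the protocol's statistical monitoring guidelines when it considers ending enrolment. Three things can mislead someone who reads it alone:

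- The 0.025 limit can be taken as the risk of missing the effect the trial was built to find, when that risk is about five times larger.
- There are two interim cut-points, and they behave very differently when AAT adds nothing.
- A final count of 6 or 7 carries a label that reads as acceptance of a rate of 16.7% or less, although the data at those counts are also compatible with the 50% target.

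With 20 patients, one or two successes decide which reading applies.

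**Working it through.** **Inputs.** n = 20, p0 = 0.167, one-sided 2.5% and design rate 0.50 (Section 10.3.1); futility rate 0.60, error limit 0.025, interim at n = 10, cut-points ≤1 or ≤2 of 10 and ≤7 of 20 (Section 10.4 and Table 10).

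**Formula.** P(X ≤ k) = Σ C(n, j) p^j (1 − p)^(n−j), summed over j = 0 to k.

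**1. Reproduce the plan's rule and power.**
- At p0 = 0.167: P(X ≥ 7) = 0.0375 and P(X ≥ 8) = 0.0114. The 2.5% test therefore rejects H01 at 8 or more, and ≤7 is its complement.
- Exact power of this rule at 45%, 50%, 55% and 60% is 74.8%, 86.8%, 94.2% and 97.9%. This matches Table 7. (Section 10.3.1 mentions asymptotic normality, but a normal approximation gives 93.5% at 50%, so the table is exact.)

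**2. Type II error at n = 20, without an interim stop.**
- At 60%: P(X ≤ 7) = 0.0210, within 0.025.
- At 50%: P(X ≤ 7) = 0.1316, the complement of 86.8%. Ratio to the stated limit: 0.1316 / 0.025 = 5.3.

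**3. Type II error if the interim stop is followed.** With a stop at ≤c of 10, error = 1 − Σ P(X1 = x) · P(X2 ≥ 8 − x), summed over x = c + 1 to 10, where X1 and X2 are the counts in each half.

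| Interim stop | Error at 50% | Error at 60% | P(stop) at 16.7% | P(stop) at 50% |
|---|---|---|---|---|
| ≤1 of 10 (Table 10) | 1 − 0.8667 = 13.3% | 1 − 0.9784 = 2.16% | 48% | 1.1% |
| ≤2 of 10 (text) | 1 − 0.8501 = 15.0% | 1 − 0.9716 = 2.84% | 77% | 5.5% |

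The text's cut-point breaks the 2.5% limit even at 60%; Table 10's does not.

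**4. Where the interim numbers could come from.** Taking each look alone at 0.025, the largest exact cut-point at n = 10 is ≤2 against 60% (0.0123) and ≤1 against 50% (0.0107; ≤2 would give 0.0547). The Emerson-Fleming boundary parameters are not given, so the intended value cannot be recovered.

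**5. What the final counts exclude (exact 95% intervals).**
- 5/20: 8.7% to 49.1%; P(X ≤ 5 at 50%) = 0.0207.
- 6/20: 11.9% to 54.3%; P(X ≤ 6 at 50%) = 0.0577; one-sided p against 16.7% = 0.103.
- 7/20: 15.4% to 59.2%; P(X ≤ 7 at 50%) = 0.1316; one-sided p against 16.7% = 0.0375.

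Only 5 or fewer excludes 50%. If the true rate is 50%, a count of 6 or 7 has probability 0.1316 − 0.0207 = 0.111.

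**The case against.** A reader might infer that choosing 60% is what turns 6 or 7 of 20 into a failure. The documents do not support that. The ≤7 boundary follows from p0 = 0.167 and the 2.5% level alone. Six and seven miss the primary test (p = 0.103 and 0.0375) whatever value H02 takes, and the stated 87% power already carries that loss.

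A reader might also infer that 0.025 contradicts the 13% implied by 87% power. It does not. They are the errors of one rule at two true rates, and Table 7 prints both as power (98% and 87%).

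Nor is 0.60 an arithmetic slip. The rule of 8 or more has 97.5% power at a true rate of 59.2%, so at n = 20 a count of ≤7 both fails to reject H01 and rejects H02 at 0.025. That this was the intent is an inference, since the protocol does not say so. Moving H02 to 0.50 would be a design preference, not a correction.

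Finally, *Accept* is common shorthand in decision tables, and nothing in the plan says that 7/20 would be reported as proof of no effect.

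All of this stands. It leaves untouched the error limit with no rate attached, the conflicting interim cut-points, and a final row whose label differs from the text's own definition of the column.

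**Conclusion.** The point holds as a defect of statement and consistency in Section 10.4. The efficacy rule is sound and reproduces the plan's power. What needs correcting is:

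- the 0.025 limit, which is true at 60% (2.1%) but not at the 50% design rate (13.2%, or 13.3% to 15.0% with the interim stop);
- the interim cut-point, where ≤2 in the text conflicts with ≤1 in Table 10 and gives 2.84% at 60%;
- the *Accept H01* label, which covers 6 and 7 of 20 although neither count excludes the target.

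The figures assume independent patients with a common rate, all 20 evaluable at day 75, and, for the two-stage values, that a futility recommendation is followed. I read the type II sentence as the risk of failing to reject H01 when H02 is true, because it directly follows the definition of H02. The effect on overall power is small (86.8% falls to 86.7% or 85.0%), so this is a clarification to settle before the first interim analysis and not a flaw that undermines the design.

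**What to change.** In Section 10.4 and Table 10:

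1. Keep 8 or more of 20 as the rule that rejects H01.
2. Replace *Accept H01* with *do not reject H01*, align the row label with the text's definition of the column, and state that 6 or 7 of 20 does not exclude the 50% target; only 5 or fewer does.
3. Restate the type II error as about 13% at 50% and about 2% at 60%, then update both for the interim cut-point kept (13.3% and 2.16% with ≤1; 15.0% and 2.84% with ≤2).
4. Reconcile ≤1 and ≤2 of 10, and derive the one kept from a stated hypothesis, error level and boundary.
5. Either justify 0.60 or say plainly that rejecting H02 does not exclude the 50% design rate.

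The cost is a protocol or SAP amendment of wording and one cut-point. No patients are added and the type I error stays under control (at most 0.0114). The downside is that the stated type II error looks less favourable.

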
I confirm that I have read the above protocol in the latest version. I understand it, and I will work according to the principles of current Good Clinical Practice (cGCP) as described in the United States Code of Federal Regulations (CFR) – 21 CFR Parts 45, 50, 56, and 312, and the International Conference on Harmonization (ICH) document “Guidance for Industry: E6 Good Clinical Practice: Consolidated Guidance” dated April 1996. Further, I will conduct the study in accordance with local, legal, and regulatory requirements.
 
As the site Principal Investigator, I agree to conduct protocol, “Efficacy of AAT in Islet after Kidney Transplantation,” according to good clinical practices. I agree to carry out the study by the criteria written in the protocol and understand that no changes can be made to this protocol without written permission of the sponsor.
 <hr/> 
Site Principal Investigator (Print)
 <hr/> 
Site Principal Investigator (Signature)
 
Date
	

Protocol Synopsis

Title	Multicenter Trial of the effect of AAT on Islet Transplant Engraftment and Durability after Renal Transplant
Short Title	Efficacy of AAT in Islet after Kidney Transplantation
Clinical Phase	Phase 2
IND Sponsor	[name]
IND Number	BB-IND 13804
Activation Date	Proposed 12/2016
Accrual Objective	20 transplanted (up to 28 transplant eligible)
Accrual Period	3 years
Study Duration	5 years (Accrual plus follow-up)
Study Design	Prospective, multi-center, trial assessing the benefit of alpha-1 antitrypsin (AAT) on islet transplantation in type 1 diabetic (T1D) kidney transplant recipients.
Treatment Description	Patients meeting the study entry criteria will receive 1-3 infusion(s) of in vitro cultured islets. Patients will receive three times a week AAT infusions in the peri-transplant period for three weeks. For the first islet transplant, patients will receive induction therapy with rabbit anti-thymocyte globulin (ATG, 6 mg/kg total in 5 doses) plus etanercept and will remain on their calcineurin-based maintenance immunosuppression regimen already in place for their renal allograft. Induction therapy will be basiliximab instead of ATG for 2 nd and 3 rd transplants, if applicable.

Primary Endpoints

The proportion of GLASSIA versus control subjects from CIT-06 achieving insulin independence at day 75 after the first infusion of single donor islets.

Secondary Endpoints

Insulin Utilization

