7.5 Follow-up Visits

Islet transplant recipients will undergo a minimum 36-month follow-up period following the last islet transplant to include time points relevant to the initial transplant. The timing of all follow-up assessments will “reset” with additional transplants; *i.e.*, the day of the 2nd transplant becomes day 0 and the subsequent assessments are conducted in relation to this day. Please refer to the Appendix 1, SOE, for the clinical time points of specific follow-up study procedures.

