7.6.2 Third Islet Transplant Criteria

The option of a third islet transplant under this protocol will be considered only if all of the following conditions are met:

1. The subject received greater than 4,000 IEq/kg following the second transplant, but remains dependent on insulin for longer than one month after the second transplant.
2. There is evidence of partial islet graft function at one month.
3. The Protocol Chair, and the Site Principal Investigators (PIs), determined that there were no relevant protocol deviations at the site.
4. The subject has been compliant with study monitoring and prescribed immunosuppressive therapy.
5. No evidence of a serious and life-threatening infection, AE, or other condition that precludes attempting an intraportal injection or continuation of the post-transplant treatment regimen.
6. Subject has no unresolved SAEs.
7. No evidence of PTLD, requiring complete withdrawal from immunosuppressive therapy.
8. No evidence of hypersensitization, allergic responses, or other potentially serious drug reactions to medications required by the protocol.
9. Stable renal function as defined as being a creatinine of no more than one third greater than the average creatinine determination performed in the 3 previous months, until rejection, obstruction or infection is ruled out.
10. Absence of anti-HLA antibodies directed to the kidney transplant or to the current islet preparation detected by Luminex Single Antigen/specificity bead assay (including weakly reactive antibodies that would not be detected by a flow cross-match). All kidney and currently-proposed islet preparation donor specificities must be avoided in 2nd and 3rd islet transplants.

Subjects who have completed 8 months follow-up post-initial transplant will no longer be eligible for additional islet transplants funded under this protocol.

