10.2.5 Study Completion

The percent of subjects who complete the study, losses to follow-up, times to lost to follow-up, and reasons for discontinuation (e.g., AEs) will be presented.

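### Section 10.4 gives two different futility cut-points for the same interim look (2 of 10 in the text, 1 of 10 in Table 10) and ties a day-75 look to study completion

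*Combined protocol and SAP*

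**What the plan says.** Section 10.4 sets one interim look for futility at 10 subjects and a final analysis at 20, with no stopping for efficacy. The monitored quantity is the insulin independence rate 75 days after the first infusion. The futility hypothesis H02 is p ≥ 0.60.

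**Cut-point.** The text says that the third column of Table 10 "provides the largest number of observed 75 day insulin independence that would lead to recommending futility". The row for 10 patients (reject H02) reads 1 or fewer, and the row for 20 patients (accept H01) reads 7 or fewer. The paragraph before the table says that "the monitoring plan would recommend for futility if no more than 2 of the first 10 transplant subjects" are insulin independent at 75 days.

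**Error limit.** "The type II error (accepting the null hypothesis when it is false) is no greater than 0.025".

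**Trigger.** "an interim analysis is planned when 10 subjects have completed the study"; the cut-point sentence repeats this condition.

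**Meaning of completion.** Section 10.4 does not define it. Section 10.2.5 lists "The percent of subjects who complete the study, losses to follow-up, times to lost to follow-up, and reasons for discontinuation", which sets completion against loss to follow-up and discontinuation. The secondary endpoints run to day 730. The synopsis gives 3 years of accrual within a 5-year study, which leaves 24 months for the last subject. Section 7.5 says that "Islet transplant recipients will undergo a minimum 36-month follow-up period following the last islet transplant".

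**The concern.** The text and the table describe the same look, the same count and the same action with different thresholds. If 2 of the first 10 subjects respond, one tells the DSMB to recommend futility and the other does not. Choosing between them after seeing the data, in an open-label trial, would defeat the purpose of a pre-specified boundary.

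The trigger raises a separate problem. A futility look is useful while there are still transplants to be avoided. The rule counts an outcome known at day 75, so waiting for full follow-up adds nothing to the decision and may remove its purpose.

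**Working it through.** **Inputs.** N = 20, null rate 0.167, one-sided 2.5%, design rate 0.50 (Section 10.3.1); cut-points, H02 at 0.60, limit 0.025, exact binomial (Section 10.4); 3-year accrual (synopsis).

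**The plan's own figures.** Success needs at least 8 of 20: P(X ≥ 8 | 20, 0.167) = 0.0114, whereas P(X ≥ 7) = 0.0375 exceeds 0.025. Exact power is 0.748, 0.868, 0.942 and 0.979 at true rates of 45, 50, 55 and 60%. This matches Table 7 (75, 87, 94, 98%). Table 10's final row fits too: P(X ≤ 7 | 20, 0.60) = 0.0210 and P(X ≤ 8 | 20, 0.60) = 0.0565.

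**Chance of a futility recommendation at the interim**, P(X ≤ k | 10, p):

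| True rate | k = 1 | k = 2 | Exactly 2 of 10 |
|---|---|---|---|
| 16.7% | 0.4834 | 0.7743 | 0.2909 |
| 50% | 0.0107 | 0.0547 | 0.0439 |
| 60% | 0.0017 | 0.0123 | 0.0106 |

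**If the trial continues from 2 of 10**, it needs at least 6 of the next 10 to reach 8 of 20. That probability is 0.377 at a true 50% and 0.0025 at 16.7%.

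**Which cut-point fits 0.025.** Read the limit as the chance of wrongly rejecting H02 at p = 0.60 and count 7 or fewer of 20 as futility at the end. Over both looks the chance is

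1 − Σ (x = k+1 to 10) P(X₁₀ = x) · P(Y₁₀ ≥ 8 − x), with X and Y binomial(10, 0.60).

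This gives 0.0217 for k = 1 and 0.0284 for k = 2. Only k = 1 stays within 0.025.

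**Boundary shape.** A two-look O'Brien-Fleming-type boundary at 0.025 allows about 0.0026 at the first look and 0.0240 at the second. That gives 1 of 10 (0.0017) and 7 of 20 (0.0210), the pair in Table 10. A Pocock-type boundary allows 0.0147 at each look. That gives 2 of 10 (0.0123), but at the end only 6 of 20 (0.0065), because 0.0210 exceeds 0.0147. The pair of 2 and 7 comes from neither.

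**Power at a true 50% if the rule is followed:** 0.8684 with no look, 0.8667 with k = 1, 0.8501 with k = 2.

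**Delay under the literal trigger.** With day 730 as the end of follow-up: (730 − 75) / 30.4375 = 21.5 months. With 36 months and a single transplant: (1095 − 75) / 30.4375 = 33.5 months. Section 7.5 counts from the last transplant, so repeat infusions lengthen this.

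**Calendar, assuming even accrual of 20 over 36 months (one per 1.8 months).**
- 10th transplant: 10 × 1.8 = month 18.
- Day-75 look: 18 + 2.5 = month 20.5, with 11 transplanted and 9 first transplants to come. After a 2-month lag for data and DSMB review, 8 remain; after 3 months, 7.
- Literal look: 18 + 24 = month 42, or 18 + 36 = month 54. The last first transplant is at month 36, so none remain.
- Repeat infusions: Section 7.6.2 says "Subjects who have completed 8 months follow-up post-initial transplant will no longer be eligible for additional islet transplants". Subjects 19 and 20 (months 34.2 and 36) stay eligible until months 42.2 and 44. At month 42 the look could affect only those two; at month 54, nobody.

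On the 24-month reading, first transplants would remain only if the 10th and 20th were more than 24 months apart, against 18 under even accrual.

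**The case against.** The contradiction itself is not in dispute, but the choice of 1 of 10 can be challenged. As worded, the 0.025 sentence concerns accepting a false null, so it must be reread before it selects anything. The final row is labelled as accepting H01, and 7 is also the largest count that fails to reject H01 at 2.5%, so that row does not prove that the limit was spread over both looks. Taken one look at a time, the largest count at n = 10 with probability at most 0.025 under p = 0.60 is 2 (0.0123; 0.0548 for 3), which is the value in the text. Section 10.4 names the Emerson and Fleming method but no boundary shape. These points stand: 1 of 10 is the better-supported value, not one the text proves. Still, 1 of 10 meets 0.025 per look and over both looks, whereas 2 of 10 meets it only per look, and the plan describes a sequential design with two analyses.

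On timing, the wording may be loose. Table 10's header refers to patients accrued, and the rule counts the first 10 transplanted, so day 75 may have been meant. In that case there is no delay, only a wrong sentence. The two problems also limit each other: under the literal trigger the cut-point hardly affects enrolment, so their full effects cannot be added.

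The practical impact is bounded. The rule is a recommendation, type I error is not inflated, and Section 6.2.1 provides other grounds for suspension. None of those replaces the futility rule.

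**Conclusion.** The concern holds; the section is wrong as written and must be corrected. The cut-point conflict needs no assumption. It changes the chance of an interim futility recommendation from 48.3% to 77.4% if AAT does nothing and from 1.1% to 5.5% at the design rate. It becomes an outright contradiction at exactly 2 of 10 (29.1% and 4.4%). The preference for 1 of 10 rests on reading 0.025 as wrong rejection of H02 at p = 0.60 and on counting the final row as futility. The delay of 21.5 months or more rests on the literal trigger; the finding that no first transplants would remain also rests on roughly even accrual.

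**What to change.** Change three sentences in Section 10.4:

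1. Cut-point: state 1 or fewer of 10 in the text, as in Table 10. If the sponsor prefers 2, the boundary shape and error definition must be given and Table 10 re-derived to match.
2. Error limit: define 0.025 as the probability of rejecting H02 when p = 0.60, over both analyses.
3. Trigger: hold the interim look when the first 10 transplanted subjects have reached the day-75 assessment after their first infusion. Use the same condition where the cut-point sentence repeats the trigger.

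The cost is an amendment under Section 10.5, preferably before any interim data are seen, and an earlier DSMB data cut. No new data are collected. Power at 50% is 86.7% with this look and 86.8% without one.
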